## **5.0 Procedures Involved**

**Study Design:**

This is a randomized, double-blind, placebo-controlled clinical trial in 40 adults at least 18 years of age with SCI. Participants who meet the eligibility criteria (described in Section 8.1) will be randomly assigned with a 1:1 ratio to active drug (escalating brivaracetam dose to 100 mg twice daily for four weeks) or placebo using a randomization schedule developed by our biostatistician. This is a simple computer generated 1:1 scheme that randomly assigns participants to arm C or arm D. Study participants, research coordinators, and study personnel involved in outcomes assessments and analyses will all be masked to allocation. The drug will be provided by RxArtisans pharmacy in Wayzata, MN. The active and placebo capsules will have identical appearance and consistency. Treatment assignment will be known only to the investigational drug pharmacy (RxArtisans). We will register this trial at [www.clinicaltrials.gov](http://www.clinicaltrials.gov).

Study Procedures:

Overview of study procedures/study interventions. This study involves research activities that occur in-person, over the phone, and via online REDCap surveys. Participants will also have the option to participate entirely remotely. In this circumstance, there will be no MRI scan nor blood draw for banking; instead, all required safety labs will be completed with the participant's primary care physician and insurance will be charged and the participant will be responsible for any associated copays or costs. All research activities are summarized in Table 1 below and described in detail in the subsequent text.

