Screening: A phone screen will be administered to confirm basic eligibility criteria listed in Section 8.1 such as age, pain level, medication use, and other medical conditions. Study staff will also screen for MRI contraindications at that time with the Center for Magnetic Resonance Research (CMRR) pre-screening questionnaire (i.e., implanted medical devices or retained metal fragments). Eligible individuals will be required to receive medical clearance from their primary care provider within one month of (prior to) Visit 1, including physical exam, health history, and lab work to confirm normal renal function, absence of liver cirrhosis, and absence of pregnancy. While we will target obtaining lab work within 1 month of baseline, labs up to 6-weeks prior to baseline will be accepted to reduce participant burden. Their insurance will be charged, and they will be responsible for any associated copays or costs.

For participants who recently had comprehensive metabolic panel done, medical record review of lab results can replace new screening labs if the blood labs were completed within one month of (prior to) the scheduled baseline appointment. If the participant is seeing a provider in-system, the study coordinator will pull labs from the medical record. If the participant is not seeing a provider in-system, the study coordinator will instruct the participant's physician to fax the lab report to the study coordinator. The instructions for faxing will be on the screening eligibility sheet the participant brings to their doctor's appointment and available to be emailed for the participant upon request.

Visit 1: This visit includes informed consent, randomization, a focused physical exam, and a mental health and health history screen. CDE-recommended questionnaires relating to pain, mood, active suicidality, satisfaction with life, kinesiophobia, sleep quality, and community integration will also be administered.

Visit 2: This visit may be combined with Visit 1, if the participant prefers. Visit 2 includes an optional blood draw for batch analysis and an optional MRI scan; the optional MRI and optional blood draw are paid for by the study. Visits 1 and 2 can take place either at the study site or virtually, depending on participant preference. Those who choose to participate in the study virtually will not take part in the MRI or blood draw. For participants with contraindications to MRI, the MRI will not be completed.

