## 8.0 Study Population

Inclusion Criteria:

- 18 years of age or older
- Injured for  $\geq 3$  months
- Completed inpatient rehabilitation and living in the community
- Chronic sublesional neuropathic pain defined as persistent pain (VAS grade 3-10) for three months or more
- For people of child-bearing potential: currently practicing an effective form of two types of birth control (defined as those, alone or in combination, that result in a low failure rate (i.e., less than 1% per year) when used consistently and correctly).

Exclusion Criteria:

- Progressive myelopathy secondary to posttraumatic cord tethering or syringomyelia
- Active use of drugs known to interact with brivaracetam: rifampin, carbamazepine, sodium oxybate, buprenorphine, propoxyphene, levetiracetam, and phenytoin.
- Brain injury or cognitive impairment limiting the ability to follow directions or provide informed consent
- Pregnancy or lactation
- Epilepsy or active treatment for seizure disorder
- Past or current suicidality
- Active treatment for psychiatric disease
- Drug addiction
- Moderate or heavy alcohol intake (up to four alcoholic drinks for men and three for women in any single day, and a maximum of 14 drinks for men and 7 drinks for women per week)

- Hepatic cirrhosis, Child-Pugh grades A, B, and C
- Impaired renal function (GFR<60ml/minute)
- Contraindications to brivaracetam or pyrrolidine derivatives including allergy
- Active clinically significant disease (e.g., renal, hepatic, neurological, cardiovascular, pulmonary, endocrine, psychiatric, hematologic, urologic, or other acute or chronic illness) that, in the opinion of the investigator, would make the patient an unsuitable candidate for this trial.
- History of malabsorption or other gastrointestinal (GI) disease that may significantly alter the absorption of brivaracetam
- Use of any investigational drug 30 days prior to enrollment in this study
- Dependent on mechanical ventilation.
- Use a gastrostomy tube (G-Tube) for feeding.
- Enrollment in another clinical trial.

People with contraindications to MRI including retained bullet fragments, noncompatible metal implants, and implanted devices such as non-MRI compatible baclofen pumps may still be eligible for the study; they will not participate in the MRI scans.

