### 15.2 Power Analysis:

We present power and sample size analysis for the primary endpoint; a 2-point improvement in neuropathic pain intensity as assessed by the

International Spinal Cord Injury Pain Basic Dataset. We based our sample size calculation on variations in pain intensity observed in an ongoing clinical trial (DoD W81XWH-14-SCIRP-CTA, [name] PI). In this sample, average neuropathic pain intensity in 28 adults with SCI was  $3.43 \pm 3.17$ . Based on this, a sample size of 20 per arm will have more than 80% power to detect a significant difference in pre-post changes of neurological pain between the two arms at a two-sided significance  $\alpha$  level of 0.05. This sample size is sufficient to address the exploratory analyses proposed in Aims 2-3.

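### Section 15.2 calls 20 per arm sufficient for Aims 2-3, but MRI and biomarker blood are optional and unavailable to some participants, so the design does not deliver those data on 20 per arm

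*Combined protocol and SAP*

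**What the plan says.** Section 15.2 (Power Analysis) contains one calculation, for the pain endpoint: "a sample size of 20 per arm will have more than 80% power to detect a significant difference in pre-post changes". It then extends that number to the imaging and biomarker aims: "This sample size is sufficient to address the exploratory analyses proposed in Aims 2-3". No separate calculation is given for those aims.

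The schedule in section 5.0 makes the data for those aims conditional:

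- Any participant may take part wholly remotely. The study overview says of this: "In this circumstance, there will be no MRI scan nor blood draw for banking". The Visit 2 text repeats it: "Those who choose to participate in the study virtually will not take part in the MRI or blood draw".
- For those who attend, the Visit 2 and Visit 3 descriptions and Table 1 mark both MRI and biomarker blood as optional.
- People with retained fragments, incompatible implants or incompatible pumps can join the trial, but under section 8.0 "they will not participate in the MRI scans".

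Section 10.0 enrols up to 48 and expects 20% attrition, which it equates to 40 completers. Section 1.1 labels Aims 2 and 3 exploratory. Section 3.0 nevertheless lists brain activity and connectivity among the secondary outcomes, and section 15.3 plans between-arm tests of their pre-post change.

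**The concern.** The sufficiency statement takes the number derived for pain, which every participant can report, and applies it to measurements that some participants cannot or need not provide. The protocol sets no target or minimum number with MRI or blood, does not enlarge enrolment for non-uptake, and does not say how missing scans or samples are handled. The allowance in section 10.0 covers attrition only.

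The trial is described as a pilot whose results will shape larger trials. If the plan is on record as adequately sized for Aims 2-3, a null imaging or microRNA result may be given more weight than the measured numbers justify. The results would also describe in-person volunteers, and for Aim 2 only those who can be scanned, rather than everyone randomised.

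**Working it through.** **1. The plan's own figure.** Section 15.2 gives a difference of 2 points ("a 2-point improvement in neuropathic pain intensity as assessed by the"), an SD of 3.17 around a mean of 3.43 ("average neuropathic pain intensity in 28 adults with SCI was"), n = 20 per arm and two-sided 5%. By the normal approximation, power = Φ(δ / (σ√(2/n)) − 1.96) = Φ(2 / (3.17 × 0.316) − 1.96) = Φ(0.035) = 51%; a two-sample t-test gives 49%. The stated figure of more than 80% needs an SD of change of about 2.26 or less. With SD of change = 3.17√(2(1 − ρ)), that means a pre-post correlation of about 0.75 or more, which is not stated. This is a separate matter and the present point does not depend on it. It does show that section 15.2 holds nothing about imaging or microRNA from which sufficiency could be derived.

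**2. The most the design is expected to deliver.** From section 10.0, 48 × (1 − 0.20) = 38.4 completers, or 19.2 per arm under 1:1 allocation. To retain 40 at 20% attrition would take 40 / 0.80 = 50 enrolled. So at full uptake the expected number of completers with data is about 19 per arm. Section 5.0 expects just over 95% of imaging data to be usable, a further small loss for Aim 2.

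**3. What smaller numbers would mean.** No uptake rate is given, so the numbers per arm below are assumptions. The detectable standardised difference d solves 80% power for a two-sample t-test at two-sided 5%. The detectable correlation is r = tanh((1.960 + 0.842) / √(n − 3)), with n the number in one arm. The third column takes the effect that has 80% power at 20 per arm (d = 0.909) and gives its power at the smaller number.

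| n per arm | detectable d | power for d = 0.909 | detectable r within one arm |
|---|---|---|---|
| 20 | 0.91 | 80% | 0.59 |
| 19 | 0.93 | 78% | 0.61 |
| 15 (75% of 20) | 1.06 | 67% | 0.67 |
| 10 (50% of 20) | 1.32 | 49% | 0.79 |

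For example, at n = 10, r = tanh(2.802 / √7) = tanh(1.059) = 0.79. None of these figures allows for multiple brain regions or multiple microRNAs, so they are optimistic for the analyses planned in sections 15.1 and 15.3.

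**4. Which data each analysis needs.** These differ, so there is no single subset for Aims 2-3:

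- Baseline miR-485 as a predictor of pain change (the working hypothesis of Aim 3 in section 1.1): Visit 2 blood and pain scores.
- Change in microRNA expression: blood at Visits 2 and 3.
- Change-score tests on MRI (section 15.3): scans at Visits 2 and 3.
- Mixed-effects models on MRI (section 15.3): these can use participants with one scan.

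MRI contraindications reduce the Aim 2 numbers but not the blood numbers.

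**The case against.** The strongest reply is that both aims are labelled exploratory, the trial is called a pilot, and the disputed sentence speaks of exploratory analyses without claiming 80% power. That stands as far as importance goes: formal power is not required for these aims, and the detectable differences above are a yardstick the plan did not set. It does not justify asserting adequacy with no calculation, least of all for brain measures that are listed secondary outcomes with planned between-arm tests.

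Several stronger readings are tempting, and the documents do not support them:

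- *Far fewer than 20 per arm will be measured.* Uptake is unknown. With 48 enrolled, about 24 per arm start, so baseline blood alone could reach 20 per arm. Table 1 also schedules the Visit 3 assessments at early withdrawal, which could recover some data from non-completers. Fewer than 20 is the reasonable expectation, not a documented count.
- *A second MRI opt-in occurs after treatment and can bias the comparison.* The section 5.0 text on the Center for Magnetic Resonance Research describes one consent leading to both scans, and MRI willingness and contraindications are raised at phone screening, before randomisation. Ordinary refusal or dropout at Visit 3 remains possible, as for any outcome. Under intact blinding, arm comparability at baseline within the subset is not obviously threatened.
- *Aims 2-3 rest on paired data throughout.* They do not: the main Aim 3 association needs only baseline blood, and the mixed models can use single scans. A paired-only rule would discard usable data.
- *The subset is wholly self-selected.* MRI contraindications are not a choice.
- *The consent form lacks an opt-in field.* Consent pages are not in the public copy, so this cannot be said.

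**Conclusion.** The sentence in section 15.2 is wrong as written. It relies on 20 per arm, while the plan's own enrolment and attrition figures give about 19 completers per arm at full uptake, and optional procedures, remote participation and MRI contraindications can only lower that. How much lower is not documented. If 15 or 10 per arm provide data (assumed values), the detectable standardised difference rises from 0.91 to 1.06 or 1.32; the detectable within-arm correlation rises from 0.59 at n = 20 to 0.79 at n = 10, before any multiplicity correction. These figures assume equal arms, two-sided 5% and 80% power.

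The consequences are loss of precision, narrower generalisability, and possible uneven loss of Visit 3 data between arms. The primary pain comparison is unaffected. Because the aims are exploratory, the remedy is an accurate statement of what they can show, not a larger trial.

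**What to change.** 1. In section 15.2, replace the sufficiency sentence with a statement that Aims 2-3 give exploratory estimates with confidence intervals in the participants who provide the data, that this is expected to be fewer than 20 per arm, and what effect is detectable over a range of uptake such as the table above.
2. Define the data for each analysis: Visit 2 blood plus pain change for the baseline miR-485 association; paired blood for microRNA change; paired MRI for the change-score tests; all available scans for the mixed model.
3. Record MRI and blood opt-in at Visit 1 before allocation, if the consent form does not already do so, so that these populations are fixed before treatment.
4. Report missing Visit 3 scans and samples by arm, and compare baseline characteristics of those with and without MRI or blood.

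The cost is a short rewrite of section 15.2, one form field and one or two extra summary tables. No extra procedures, staff or participants are needed. The downside is that the stated adequacy for Aims 2-3 becomes less favourable.

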### 15.3 Statistical Analysis:

All statistical analyses will be conducted with Stata v. 17.0 or SAS v.9.4.72 assuming a 5% level of significance unless otherwise stated. Participant characteristics will be described using frequency counts and percentages (nominal variables) and means/standard deviations (SDs) or medians and interquartile ranges (IQRs) (continuous variables). Chi-square tests and t-tests or rank-sum tests will be used to compare the subject characteristics between the treatment arms.

#### Aim 2 statistical analysis

fMRI data will be processed using the conn functional connectivity toolbox with established standardized controls for multiple comparisons (SPM family wise error correction methods). Data will undergo realignment, scrubbing, artifact detection, and CompCor denoising. Primary analyses will focus on OP1/OP4 and insula regions-of-interest for resting-state connectivity and exploratory multivariate pattern analyses. Task-based fMRI will undergo the same preprocessing pipeline and will be modeled with a general linear model. Within-group pre-post changes in task-based brain activation and resting-state connectivity will be tested using paired t-tests or Wilcoxon signed-rank tests.

Between-group differences of pre-post changes in these measures will be tested using 2 sample t-tests or Mann-Whitney U tests. Mixed effects models with correlated errors will also be used to test the effect of CMR on brain imaging outcomes after adjusting for potential confounders, which will include the subject-level effect, time, group indicator, and time-by-group interaction as predictors, and age, race, and other covariates as appropriate. We will use False Discovery Rate (FDR) correction to control for the overall Type 1 errors for the voxel-level analyses. We will test the correlation between changes in brain function and clinical measures of sensory and

motor function using Pearson's correlations coefficients with 95% confidence interval calculated based on Fisher's Z transform.

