**Use of radiation: N/A**

**Use of Center for Magnetic Resonance Research:**

All participants who consent to MRI testing will get a 3T structural and functional MRI scan at Visit 2 and after completion of the 7-week treatment course (Visit 3). They will use the changing room to change into scrubs according to the CMRR protocol.

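### In the two-visit Aim 2 mixed model, age and race entered as main effects cannot adjust the treatment effect on change in participants with both scans, so the stated confounder adjustment is not obtained

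*Combined protocol and SAP*

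**What the plan says.** Section 15.3 (Aim 2 statistical analysis) gives two between-arm analyses of the imaging measures. The first is unadjusted: "Between-group differences of pre-post changes in these measures will be tested using 2 sample t-tests or Mann-Whitney U tests". The second is additional: "Mixed effects models with correlated errors will also be used", to test the intervention effect "on brain imaging outcomes after adjusting for potential confounders". Its terms are "the subject-level effect, time, group indicator, and time-by-group interaction as predictors, and age, race, and other covariates as appropriate". (The sentence names the intervention as CMR; I read it as the study treatment.)

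No covariate-by-time term is listed. The text does not say in words how age and race enter, which other covariates are meant, what error structure is used, or how participants with one scan are handled.

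Section 5.0 (Use of Center for Magnetic Resonance Research) fixes the number of imaging occasions: participants who consent to MRI have a "3T structural and functional MRI scan at Visit 2 and after completion of the 7-week treatment course", the second being Visit 3. The MRI is optional (section 5.0, Study Procedures).

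**The concern.** With a baseline scan and one follow-up scan, the treatment effect on change is the time-by-group coefficient. A covariate that is constant within a person and enters as a main effect shifts both scans by the same amount. It can explain differences in level between people, but not differences in change between arms.

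Three things follow. The plan describes an adjusted treatment effect that its listed model does not produce for age and race. The unadjusted and so-called adjusted results will agree, exactly or nearly, for algebraic reasons, and a report could present that agreement as robustness to confounding. And a chance imbalance in a covariate that influences change stays in the estimate labelled as adjusted. Such imbalance is plausible here: section 5.0 describes simple 1:1 randomisation without stratification, and optional MRI may leave well under 40 people scanned.

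**Working it through.** No power or sample-size figure in the plan depends on this model, so there is no stated figure to reproduce. The check is algebra, then a numerical confirmation.

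**Algebra.** Let G be arm, X a time-fixed covariate such as age, and d the time-by-group coefficient.

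- Visit 2: Y1 = a + gG + bX + e1
- Visit 3: Y2 = a + t + (g + d)G + bX + e2
- Change: Y2 − Y1 = t + dG + (e2 − e1)

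The term bX has gone. With both scans observed for everyone analysed, and a compound-symmetric or unstructured error covariance, the estimate of d is exactly the raw difference in mean change.

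**Numerical confirmation.** Assumed settings, none from the documents except the 20 per arm of section 15.2 and the 20% attrition of section 10.0: 20 or 8 per arm, within-person correlation 0.6, unit error variance, age 0.8 SD out of balance, race also out of balance. Each setting had up to 200 simulated trials, of which 109 to 159 (those where all models fitted) were kept.

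| Setting | Result |
|---|---|
| Both scans, age and race as main effects | Differs from the raw difference in mean change by at most 2e-15; SE matches the pooled t-test SE within 1e-5 |
| 20% of second scans missing, 20 per arm | Models with and without age and race differ by 0.07 SE on average, at most 0.33 SE |
| 20% of second scans missing, 8 per arm | 0.08 SE on average, at most 0.32 SE |
| Both scans, covariate-by-time terms added | Estimate moves by 0.40 SE on average, even when age does not affect change |
| Both scans, time-varying covariate with an assumed effect of 0.4 per SD | Estimate moves by 0.40 SE on average |

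The small gap with missing scans comes from people who contribute one scan, not from adjusting change.

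**What adjustment would do.** Assume that age affects change by 0.03 per year and that the true effect is 0.50, with the same built-in age imbalance. The mean estimates are raw 0.835, main-effects model 0.835, covariate-by-time model 0.551. This is a constructed case. It shows that the listed model leaves such an imbalance untouched, not that one will occur.

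**Precision from baseline.** This is a separate matter from the cancellation. Let r be the correlation between the Visit 2 and Visit 3 measures, which the documents do not give. With equal variances at the two visits, the change score has variance 2(1 − r) and the baseline-adjusted outcome 1 − r², so the ratio is (1 − r²) / [2(1 − r)] = (1 + r)/2, that is 0.65, 0.75 and 0.85 at r = 0.3, 0.5 and 0.7.

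Assume a 0.8 SD difference, 15 per arm and two-sided 5%. The standardised effect is 0.8/√[2(1 − r)] = 0.676, 0.800, 1.033 for change and 0.8/√(1 − r²) = 0.839, 0.924, 1.120 with baseline. Power from the noncentral t:

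| r | Change score (28 df) | Baseline only (27 df) | Baseline plus two covariates that predict nothing (25 df) |
|---|---|---|---|
| 0.3 | 43% | 60% | 55% |
| 0.5 | 56% | 68% | 63% |
| 0.7 | 78% | 84% | 79% |

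The last column also charges the usual variance inflation for chance covariate imbalance, 1 + 3/(30 − 2 − 3 − 1) = 1.125. The same charge in the baseline-only column, 1 + 1/(30 − 2 − 1 − 1) = 1.038, would give 58%, 67% and 83%.

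**The case against.** The strongest reply is that main-effect entry is inferred. The plan leaves room for covariate-by-time terms, and section 15.1 says Aim 2 follows an approach refined in other studies that we cannot see. That stands as a limit on certainty. But the sentence names one interaction and then appends the covariates, so main effects is the natural reading; if interactions were meant, the text has to say so.

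A reader might infer that the model adjusts for nothing at all. The documents do not support that. The open-ended covariate clause could admit measures that vary by visit: head motion is tracked for each scan, and pain, alcohol, caffeine and tobacco are asked about beforehand. Section 15.3 does not name these as covariates, but they would not cancel. The finding covers age, race and other time-fixed covariates.

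A reader might also infer that the model is merely the t-test again. That is exact only with complete pairs. MRI is optional, section 10.0 expects 20% attrition, and section 5.0 expects over 95% usable data rather than all. A mixed model keeps one-scan participants; a t-test of changes cannot. The resulting gap is small, and assessment at early withdrawal (Table 1, footnote c) would reduce missing scans.

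Finally, a reader might infer that the Aim 2 treatment estimate is biased or invalid. It is not: allocation is random, so the unadjusted difference in mean change is a valid estimate. Aim 2 is labelled exploratory and this model supplements the two-sample tests. It is also fair to say that the power comparison measures baseline adjustment against change scores, not the cost of age and race cancelling.

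**Conclusion.** The point holds in a limited form. On the natural reading of section 15.3, age, race and any other time-fixed covariate leave the time-by-group estimate unchanged when both scans are present, and nearly unchanged (about 0.07 SE on average in the simulations) when 20% of second scans are missing. The adjustment the plan describes is not delivered for those covariates, and agreement with the t-test of changes says nothing about confounding.

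The algebra needs no assumption beyond main-effect entry, two visits and complete pairs. The missing-scan and age-effect figures rest on the assumed simulation settings. The precision forgone by not using baseline depends on the unknown r: over r = 0.3 to 0.7 in the example, the power gain runs from 17 down to 6 points with baseline alone, and from about 12 down to about 1 point if two uninformative covariates are added. No primary-endpoint inference is affected. The change is worth making because it replaces a nominal adjustment with a real one at little cost.

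**What to change.** In section 15.3, state the adjusted Aim 2 analysis as: Visit 3 connectivity (or activation) regressed on arm, the same measure at Visit 2, age and a short list of covariates named in advance. An alternative is a longitudinal model with a common baseline mean for the two arms and covariate-by-time terms; it has the advantage of keeping participants with one scan. Retain the unadjusted comparison of change as the companion analysis, and do not present agreement between the current mixed model and that comparison as evidence of robustness.

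The edit is about one sentence and uses only data already collected. The cost is one degree of freedom per covariate, plus some variance inflation if a covariate predicts nothing. In an imaging subset that may be small, that argues for keeping the list short.
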